D.5.1. Eligibility and Baseline Assessment: The Eligibility and Baseline Assessment (EBA) will be accomplished during 1-2 visits over a 7 -day period prior to starting treatment. It will take a total of 3 hours. Provisional diagnosis of PTSD and its severity would be obtained by PCL-5 score >33 . The CAPS-5 would be then administered to establish PTSD diagnosis. The M.I.N.I. International Neuropsychiatric Interview (M.I.N.I. 6.0)(Sheehan et al., 1998) will be used for psychiatric evaluation to confirm the absence of exclusionary diagnoses. Lack of moderate/severe cognitive impairment will be ascertained with an MMSE score ≥ 28 . Evaluation of exclusionary criteria involving unstable medical illnesses will be based on brief physical examination, medical record review by study M.D. in consultation with on-site study

anesthesiologist, basic metabolic laboratory tests, and ECG. A urine pregnancy, if applicable, and drug screen will also be obtained. Secondary outcomes at baseline will include cognitive function (CogState), severity of depressive symptoms (MADRS), levels of anxiety (Beck Anxiety Inventory-BAI), suicide risk (Columbia- Suicide Severity Rating Scale- C-SSRS), pain intensity (Numeric Rating Scale-NSR for pain), clinical impression of illness severity (Clinical Global Impression-CGI) quality of life (World Health Organization Quality of Life-Brief-WHOQOL-BREF), and expectation of treatment (CEQ).

D.5.2. Treatment Assessment: The research staff will measure PTSD symptoms severity by administering the CAPS-5 at weeks 4, 12 and 2-month follow-up. Secondary outcomes that includes cognitive function, anxiety, depression, pain, suicide, and general side effects (Patient Rated Inventory of Side Effects- PRISE/ Frequency, Intensity, and Burden of Side Effects Rating-FIBSER) will be obtained 24 hrs. post-ketamine and prior to PE session at week 1, 2, and 3 (ketamine-PE phase). We will administer rating scales again at week 4, 6, 8, and 12 (ketamine-free phase), and at 2-month follow-up. Fear activation and extinction during PE sessions would be measured by the Subjective Units of Distress Scale (SUDS).

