D.5.3. Follow-up Assessment: Following completion of treatment, participants will attend Post-Treatment Assessment monthly for 2 months (total of 02 follow-up visits). Each visit will take about 2 hours. Follow-up assessments will involve self-report for PTSD symptoms (PCL-5), cognitive assessment (CogState), depressive symptom severity (MADRS), clinical impression of illness severity and improvement (CGI), as well as self-reported measures of pain intensity (NRS for pain), level of anxiety (BAI), suicide risk (C-SSRS), general adverse events (PRISE/FIBSER) and quality of life (WHOQOL-BREF). The CAPS-5 will be administered once at 2-month follow-up.

Table 5: General Assessment Schedule

Construct	Measure	Eligibility and Baseline Assessment	Treatment Assessments	Follow-Up Assessment
		1-2 weeks	Week 1 to 12	2 months
Primary Outcome Measure				
PTSD symptoms	CAPS-5	X	X	X
Interview Based Assessments				
Decision-making capacity	Dysken Screening Tool	X		
PTSD severity	PCL-5	X	X	X
Diagnostic interview for comorbid conditions	M.I.N.I.	X		
Rule-out moderate/severe cognitive impairment	MMSE	X		
Infusion Safety Measures				
Physical Exam/ECG/Pregnancy test/Urine toxicology		X		
Recovery from infusion	mAldrete		X	
Side Effects (dissociative, psychotogenic, and manic symptoms)	CADSS, BPRS+, YMRS		X	
Secondary Outcome Measures				
Subjective units of distress (a proxy for extinction)	SUDS		X	
Cognitive function	CogState	X	X	X
Depressive Symptoms	MADRS	X	X	X
Suicide Risk	C-SSRS	X	X	X
Anxiety Symptoms	BAI	X	X	X
Pain Intensity	NRS	X	X	X
Quality of Life	WHOQOL-BREF	X	X	X
General Adverse Events	PRISE/FIBSER		X	X
Global Rating of Illness Severity and Improvement	CGI	X	X	X
Credibility/Expectation of Outcome Treatment	CEQ	X		

D.5.4. Independent Evaluation Integrity: The PI will oversee assessment core to ensure that independent evaluators will 1) undergo standardized training in all assessment instruments, 2) demonstrate reliability of

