D.6.4. Side Effects Measures: We will monitor side effects during intervention and at follow-up visits. The **PRISE** (Rush et al., 2004) assess for the last 7 days the side effects in the following symptom domains; Gastrointestinal, Heart, Skin, Nervous System, Eyes/Ears, Genital/Urinary, Sleep, Sexual Functioning, and Other. Each domain has multiple symptoms which can be endorsed. The PRISE is used in combination with **FIBSER** (Wisniewski, Rush, Balasubramani, Trivedi, & Nierenberg, 2006) which rates the intensity, frequency and overall burden due to side effects in a 7-point Likert-type scale. During ketamine infusions, we will assess potential side effects by 1) the **CADSS** (Bremner et al., 1998), a clinician-administered tool validated in healthy subjects and patients with PTSD and designed to measure present-state perceptual, behavioral, and attentional alterations occurring during dissociative experiences; 2) the four-item positive symptom subscale of the **BPRS** (Zanello, Berthoud, Ventura, & Merlo, 2013) a clinician-rated tool that assess change in severity of psychopathology consisting of suspiciousness, hallucinations, unusual thought content, and conceptual disorganization; and 3) the **YMRS** (Young, Biggs, Ziegler, & Meyer, 1978), item #1 to evaluate possible manic symptoms. Finally, the **Modified Aldrete score system** (mAldrete)(Aldrete, 1995) is a set of criteria commonly used to assess transition from anesthesia to recovery. Numeric scores of 0, 1, or 2 are assigned to motor activity, respiration, circulation, consciousness, and SpO₂ level for a maximal score of 10. A score ≥ 9 is required for discharge from post-anesthesia care unit.

6.7. Data Analysis Plan.

6.7.1. Sample Details: *We propose a sample of 10 patients in this proof-of-concept pilot study.*

6.7.2. Data Collection: Study data will be collected and managed using VA REDCap (Research Electronic Data Capture) hosted behind the VA firewall on a VINCI server. REDCap is a secure, web-based application designed to support data capture for research studies, providing 1) an intuitive interface for validated data entry; 2) audit trails for tracking data manipulation and export procedures; 3) automated export procedures for seamless data downloads to common statistical packages; and 4) procedures for importing data from external sources.

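### PRISE/FIBSER has no pre-treatment administration, so new or worsened general side effects cannot be reliably told from pre-existing symptoms on this instrument

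*Combined protocol and SAP*

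**What the plan says.** Four places describe the timing of PRISE/FIBSER, and they agree.

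- **D.6.4 (Side Effects Measures)** states: "We will monitor side effects during intervention and at follow-up visits". PRISE is to "assess for the last 7 days the side effects in the following symptom domains", and nine domains follow. FIBSER is the companion scale "which rates the intensity, frequency and overall burden due to side effects in a 7-point Likert-type scale". A recall period is given for PRISE and none for FIBSER.
- **D.5.1 (Eligibility and Baseline Assessment)** begins its list with "Secondary outcomes at baseline will include cognitive function (CogState), severity of depressive symptoms (MADRS), levels of anxiety" and continues with suicide risk, pain, CGI, WHOQOL-BREF and CEQ. PRISE/FIBSER is not in it.
- **D.5.2 (Treatment Assessment)** names PRISE/FIBSER among the measures that "will be obtained 24 hrs. post-ketamine and prior to PE session at week 1, 2, and 3 (ketamine-PE phase"). It then adds: "We will administer rating scales again at week 4, 6, 8, and 12 (ketamine-free phase), and at 2-month follow-up". D.5.3 schedules two monthly follow-up visits, with "general adverse events (PRISE/FIBSER) and quality of life (WHOQOL-BREF") among the measures.
- **Table 5** marks PRISE/FIBSER under treatment and under follow-up and leaves the baseline cell empty.

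D.1 puts safety and tolerability in the first aim. Table 5 and D.5.2 class general side effects as a secondary outcome. Section 6.7.3 plans a descriptive look at change in the secondary measures. It names PCL-5, CogState and MADRS and leaves the list open.

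**The concern.** The study has one arm, so the main way to recognise a new or worsened symptom is to compare each patient with his or her own state before treatment. Table 3 admits patients on stable psychotropics, and Table 2 explains why washout was rejected, so gastrointestinal, sleep, sexual or other complaints may well be present before the first infusion. Without a baseline form, such a complaint looks the same in the data as one that began on treatment.

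The tolerability data carried into the RCT proposal would then mix the two. The independent panel that reviews adverse events after 6 subjects could not separate them from PRISE/FIBSER alone.

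**Working it through.** No sample-size or power formula applies, and the plan states no figure on this point. The check is a count from the schedules, plus the overlap of the PRISE recall window with the pre-treatment period.

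**1. Rows of Table 5.** The secondary block has 10 rows.

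| Marked for | Measures | Baseline mark |
|---|---|---|
| Treatment and follow-up | CogState, MADRS, C-SSRS, BAI, NRS, WHOQOL-BREF, CGI | yes (7) |
| Treatment and follow-up | PRISE/FIBSER | no (1) |
| Treatment only | SUDS | no |
| Baseline only | CEQ | yes |

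Two of 10 rows lack a baseline. SUDS is recorded only during imaginal exposure, which starts at Session 3, so none is expected there. Among the 8 rows marked for both later periods, the count is 1 of 8. PCL-5 is treated as secondary in D.6.3 but sits elsewhere in the table; adding it gives 1 of 9. Adding CAPS-5 as well gives 1 of 10. PRISE/FIBSER is the only exception each time.

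**2. Administrations.** Weeks 1, 2 and 3 (3), weeks 4, 6, 8 and 12 (4) and two monthly follow-ups (2) give 3 + 4 + 2 = 9. Section E does not name PRISE/FIBSER, but its payments give the same visit pattern: 75 + 3×50 + 4×30 + 2×30 = 75 + 150 + 120 + 60 = 405, the stated maximum, for one baseline and nine later assessments. If only the 2-month visit mentioned in D.5.2 is counted, the total is 8. Either way, 0 precede infusion 1.

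**3. PRISE recall window.** Assume infusions on days 0, 7 and 14, and forms exactly 24 hours later.

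- Week 1, form on day 1: covers day −6 to day 1. Pre-treatment share = (7 − 1)/7 = 6/7 = 86%.
- Week 2, form on day 8: covers days 1 to 8. Share 0/7.
- Week 3, form on day 15: covers days 8 to 15. Share 0/7.
- All later forms: share 0/7.

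The week-1 form therefore spans both sides of infusion 1, and a symptom endorsed on it cannot be placed on either side. No such figure can be given for FIBSER, because no window is stated.

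**4. Domains.** D.6.4 lists gastrointestinal, heart, skin, nervous system, eyes/ears, genital/urinary, sleep, sexual functioning and other: 9 domains. Domains with a clean pre-treatment record on this instrument: 0 of 9.

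**5. Illustration.** The documents give no background symptom rate, so the prevalences p below are assumptions. For 10 patients and no treatment effect, the expected number endorsing a symptom is 10p, and the chance of at least one is 1 − (1 − p)^10.

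| Assumed p | Expected of 10 | Chance of at least one |
|---|---|---|
| 10% | 1 | 65% |
| 20% | 2 | 89% |
| 30% | 3 | 97% |
| 50% | 5 | 99.9% |

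This shows how readily background symptoms would appear in the listing. It does not estimate an excess event rate.

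**The case against.** The strongest reply is that PRISE/FIBSER measures side effects, so comparing it with state or severity scales is not like for like. FIBSER in particular rates burden due to side effects, and before ketamine these could come only from background medication. This stands in part: a baseline FIBSER is worth less than a baseline PRISE, though it can still record the burden of existing drugs and does no harm. The other side-effect scales are also blank at baseline in Table 5, but CADSS, BPRS+ and YMRS are rated before each infusion (D.4.1, Table 4). PRISE/FIBSER has no such rating.

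A second reply is that the pilot is descriptive, has 10 patients, and does not expressly promise a change analysis of PRISE/FIBSER. That is right: such an analysis is inferred from the open-ended list in 6.7.3, and endorsements can be listed by visit without a baseline. But tolerability is in the first aim, and a listing that cannot show which symptoms are new informs the RCT poorly.

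A third is that other information exists before treatment: "brief physical examination, medical record review by study M.D"., laboratory tests, ECG, MADRS, BAI, pain NRS and WHOQOL-BREF, together with the stable-dose rule and the infusion-day monitoring. These soften the gap. None is described as a symptom record across the nine PRISE domains.

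Finally, a baseline would not attribute a symptom to ketamine rather than to PE or natural fluctuation. That is also right; it would only identify what is new or worse.

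**Conclusion.** The concern holds. The plan has no PRISE/FIBSER administration before infusion 1 (0 of 9), and this is the only one of the 8 secondary measures followed through treatment and follow-up that lacks a baseline. The table and the text agree, so this is a design gap and not a slip in one place. New or worsened general side effects cannot be reliably separated from pre-existing symptoms on this instrument.

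The zero count depends on no assumption. The 86% figure assumes a form exactly 24 hours after infusion 1; D.1 places the PE session within 24 hours, so the post-infusion part may be slightly shorter. The importance is moderate: the change should be made, but the CAPS-5 result and the acute infusion safety data do not depend on it.

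**What to change.** Add PRISE and FIBSER to the baseline column of Table 5 and to the list in D.5.1, completed before infusion 1, with the PRISE recall period unchanged. In 6.7.3, add one sentence: symptoms new or worse than baseline will be reported alongside the full listing of all endorsements. The full listing stays, so no signal is hidden. Giving both summaries to the safety panel at its review after 6 subjects is optional.

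The cost is two questionnaires at an assessment that already takes about 3 hours and is already compensated, with no extra visit, staff or procedure. The documents give no completion time. Assuming 5 to 10 minutes for both forms, the added burden is 5/180 = 2.8% to 10/180 = 5.6%. The change has to be made before a patient's first infusion, because pre-treatment status cannot be collected prospectively afterwards.

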6.7.3. Data Analysis: The data analyses will be performed by [name], Co-I on this project. Each subject will be assessed for the primary outcome variable (CAPS-5 score) at baseline (1-2 weeks prior to starting the intervention), week 4, and at the end of PE treatment (week 12). *Statistical analysis for this study will be essentially descriptive in nature. We will assess means, standard deviations, and 95% confidence intervals in symptoms at key assessment points. We will also examine distribution of missing data. In addition to the CAPS-5, we will also examine change in our secondary measures (PCL-5, CogState, MADRS, etc.), again these analyses will be descriptive in nature and will be used to refine our RCT proposal.*

6.7.4. Data Safety.

After the recruitment of 6 subjects, an independent, 3-person panel of physicians and researchers will conduct a reassessment of the risks and benefits to study participants. This panel will review all adverse events for severity and frequency.

6.8. Anticipated potential problems and alternative strategies.

The research infrastructure and SOPs to run ketamine infusions, and a well-established PTSD service are currently in place at MVA to assure timely start-up within 3 months. However, possible problems and solutions during execution of the study might be: 1) Slow recruitment/enrollment: We cautiously propose recruiting about 10 veterans aim to complete the primary outcome for our study. Nevertheless, if recruitment is slow, we would expand to include recruitment from satellites clinics within the Minneapolis VA Health Care System. In addition, we could reach out the Veteran's population served at the St. Cloud VA Health Care System (SCVAHCS) (see. 6.3.2. Feasibility of recruitment. 2) Dropouts and missing data: In our own sample, out of 16 subjects, only 2 dropped out in agreement with the literature that consistently supports tolerability of serial ketamine infusions. However, if risk of dropping out due to assessment burden occurs, subjects will have the option of completing a minimum core of primary outcome measures and maintain a flexible routine for recurrent appointments. For missing values, we will handle it by data imputation strategies, by last-

observation-carried-forward, and by the exclusion of dropouts (completers-only analyses); 3) Lost of follow-up: We would initiate outreach procedures and safety checks.

E. STUDY COMPENSATION

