Participants will be compensated for completing the assessment sessions throughout the study. Assessment sessions involve individual clinical interviews, self-report, and semi-structured questionnaires. Compensation for assessment sessions will be delivered according to the following schedule: \$75 for Eligibility Screen and Baseline (1 week prior to starting treatment, approximately 3 hours), \$50 for each assessment during medication phase (total of 03 over 3 weeks; +/- 02 hrs. each), \$30 at post-ketamine PE sessions 4, 6, 8 and 12 (total of 04 over 2 months; +/- 02 hrs. each), and \$30 for monthly follow-up post-treatment (twice for +/- 02 hrs.) for a total of up to \$405. Participants who prematurely withdraw from study assessments will not be compensated for assessment sessions that have not yet taken place.

F. BIBLIOGRAPHY AND CITED REFERENCES

Abdallah, C. G., Adams, T. G., Kelmendi, B., Esterlis, I., Sanacora, G., & Krystal, J. H. (2016). KETAMINE'S MECHANISM OF ACTION: A PATH TO RAPID-ACTING ANTIDEPRESSANTS. *Depress Anxiety*, 33(8), 689-697. doi:10.1002/da.22501

Abbott, C. S., Lim, K. O., Forbes, M. K., Erbes, C., Tye, S. J., Grabowski, J. G., . . . Shiroma, P. R. (2018). Efficacy, Safety, and Durability of Repeated Ketamine Infusions for Comorbid Posttraumatic Stress Disorder and Treatment-Resistant Depression. *J Clin Psychiatry*, 79(3). doi:10.4088/JCP.17m11634

Abbott, C. S., Shiroma, P. R., Cullen, K. R., Johns, B., Thuras, P., Wels, J., & Lim, K. O. (2017). The Antidepressant Effect of Repeat Dose Intravenous Ketamine Is Delayed by Concurrent Benzodiazepine Use. *J Clin Psychiatry*, 78(3), e308-e309. doi:10.4088/JCP.16l11277

Aldrete, J. A. (1995). The post-anesthesia recovery score revisited. *J Clin Anesth*, 7(1), 89-91.

Averill, L. A., Purohit, P., Averill, C. L., Boesl, M. A., Krystal, J. H., & Abdallah, C. G. (2017). Glutamate dysregulation and glutamatergic therapeutics for PTSD: Evidence from human studies. *Neurosci Lett*, 649, 147-155. doi:10.1016/j.neulet.2016.11.064

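### After week 4, general adverse events are asked about over 7 days at visits 2 weeks to a month apart, so cumulative counts of brief events in ketamine-free PE and follow-up would be biased low

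*Combined protocol and SAP*

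**What the plan says.** D.6.4 opens with a general commitment, "We will monitor side effects during intervention and at follow-up visits", and then says that the PRISE will "assess for the last 7 days the side effects in the following symptom domains". The PRISE is paired with the FIBSER, whose recall period is not given. Table 5 names PRISE/FIBSER, and nothing else, against general adverse events.

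The timing comes from three places:

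- **D.5.2, ketamine-PE phase:** side effects and the other secondary measures "will be obtained 24 hrs. post-ketamine and prior to PE session at week 1, 2, and 3 (ketamine-PE phase".
- **D.5.2, later phase:** "We will administer rating scales again at week 4, 6, 8, and 12 (ketamine-free phase), and at 2-month follow-up". The payment schedule in section E agrees on the treatment visits: "at post-ketamine PE sessions 4, 6, 8 and 12 (total of 04 over 2 months".
- **D.5.3, follow-up:** "participants will attend Post-Treatment Assessment monthly for 2 months (total of 02 follow-up visits", with "general adverse events (PRISE/FIBSER" among the measures at those visits.

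On use of the data, 6.7.4 sets up an independent three-person panel after 6 subjects are recruited: "This panel will review all adverse events for severity and frequency". The first aim in D.1 includes safety and tolerability of the combined ketamine and PE approach.

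**The concern.** The recall length fits the visit spacing only while visits are weekly. Once they are 2 weeks, 4 weeks and then about a month apart, a 7-day question leaves a gap before each window. An event that starts and resolves inside a gap is asked about nowhere in the schedule as written. The other side-effect scales (CADSS, BPRS+, YMRS, mAldrete) belong to infusion days, and the C-SSRS covers only suicidality.

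The weeks with gaps are not outside the safety question. Imaginal exposure starts at session 3 and continues through the ketamine-free phase, and the aim concerns the combination. With 10 patients, missing one patient's event moves a reported proportion by 1/10, or 10 percentage points. The results are also meant to refine a later randomised trial, so an undercount would carry forward.

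**Working it through.** The documents give no coverage figure, so there is nothing to reproduce. The check is a count of days.

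**Inputs.** Recall R = 7 days (D.6.4). Assessments at weeks 1, 2, 3, 4, 6, 8 and 12 (D.5.2, section E), then two monthly follow-ups (D.5.3). The length of a month is my assumption, varied below.

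**Formula.** For successive visits separated by gap g, uncovered days u = max(0, g − R). The uncovered share is Σu divided by Σg, counted from the week-4 visit to the last follow-up.

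**Weeks 1 to 4.** Each gap is 7 days, so u = 0 and coverage is complete.

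**After week 4:**

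| Assumption | Gaps (days) | Uncovered (days) | Share |
|---|---|---|---|
| 28-day months, both follow-ups | 14, 14, 28, 28, 28 | 7+7+21+21+21 = 77 of 112 | 68.75% |
| 30-day months, both follow-ups | 14, 14, 28, 30, 30 | 7+7+21+23+23 = 81 of 116 | 69.8% |
| 28-day months, 2-month follow-up only | 14, 14, 28, 56 | 7+7+21+49 = 84 of 112 | 75.0% |
| Weeks 4 to 12 only | 14, 14, 28 | 7+7+21 = 35 of 56 | 62.5% |

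The third row is there because D.5.2 mentions only the 2-month follow-up. D.5.3 and section E both give two monthly visits, so the first two rows are the main result.

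**From days to events.** An event lasting d days is wholly missed only if it starts and ends inside one gap, so its onset must fall in the first u − d days of that gap. With onset uniform over the 112 days (28-day months), the missed share is Σ max(0, u − d) / 112:

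| Duration d | Sum | Wholly missed |
|---|---|---|
| 1 day | 6+6+20+20+20 = 72 | 64% |
| 3 days | 4+4+18+18+18 = 62 | 55% |
| 7 days | 0+0+14+14+14 = 42 | 37.5% |
| 14 days | 0+0+7+7+7 = 21 | 19% |
| 21 days | 0 | 0% |

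Durations and uniform onset are assumptions; the documents give neither.

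**After the fix.** If each visit asks about the whole interval since the last one, R equals g, u = 0 at every visit, and uncovered days fall from 77 of 112 to 0 of 112.

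**The case against.** The strongest reply has four parts.

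- **The drug-exposure period is covered.** All three infusions fall in weeks 1 to 3, with weekly PRISE/FIBSER plus infusion-day scales and vital signs. D.1.1 (Table 2) puts the half-life at 186 minutes and has dissociative effects resolving within 240 minutes. This stands. The point does not concern acute ketamine tolerability.
- **Uncovered days are not missed events.** A reader might infer that 70% of adverse events after week 4 are lost. The documents do not support that: the loss depends on duration, and about four in five two-week events would still reach a window.
- **The plan specifies no cumulative adverse-event rate.** Section 6.7.3 is descriptive and works at key assessment points, and 7-day prevalence at a visit is not biased by gaps between visits. This also stands. But the panel is told to consider all events and their frequency, which a set of separate 7-day windows cannot supply after week 4. When the panel meets, the most recent of the 6 recruits may still be in the fully covered weeks, so the effect on that review may be smaller than on end-of-study counts.
- **Other routes may exist.** The opening sentence of D.6.4 is general, the panel's remit is not limited to the PRISE, patients see therapists between assessments, and 6.8 mentions safety checks for those lost to follow-up. A reader might infer that a serious event in a gap reaches the panel only if volunteered. That is an inference from silence: the attached infusion procedures and the consent pages cannot be seen here, and suicidal behaviour is tracked by the C-SSRS last-visit version. What remains is that no section shown tells anyone to ask about, record or forward general events between windows.

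**Conclusion.** The concern holds in limited form. On the stated schedule, about 69-70% of the days after the week-4 visit lie in no general adverse-event window. Cumulative counts of brief, non-suicidal events during ketamine-free PE and follow-up are therefore biased low. The size depends on duration, from roughly two thirds of 1-day events to none at 21 days. This rests on 28- to 30-day months, uniform onset, attendance at every visit, and no other collection route than those described in the text.

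It does not extend to adverse-event data as a whole: coverage through week 4 is complete, visit-level prevalence is unaffected, and the primary outcome (CAPS-5 change to week 12) is not touched. It is a worthwhile improvement to safety capture, not a fault that undermines the pilot.

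**What to change.** In D.6.4 and D.5.2-D.5.3, keep the 7-day PRISE/FIBSER as the measure of side-effect burden. At each scheduled assessment from the first infusion to the 2-month visit, add one open question on any new or worse health problem since the last visit. Record onset, end, severity and relation to study treatment. State in 6.7.4 that the panel reviews this record, and in 6.7.3 that any cumulative adverse-event frequencies come from it. The protocol already takes this approach for suicidality, with the last-visit C-SSRS.

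The cost is a sentence or two of protocol text, one short REDCap form and a few minutes at visits already planned. Reported event counts will be higher than with 7-day recall alone, which should be borne in mind in any comparison with studies that used only the 7-day form.
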